#### **4.1.6 Packaging, labelling, and re-supply**

For details of packaging and the description of the label, refer to the Investigator Site File (ISF).

#### **4.1.7 Storage conditions**

Study medication (BI 409306 or placebo) will be stored in a secure, locked compartment under the supervision of the site staff. Store tablets in the original package in order to protect them from moisture and light. For storage conditions refer to the locally approved medication label and the STORM document in the ISF.

#### **4.1.8 Drug accountability**

Drug supplies, which will be provided by the sponsor, must be kept in a secure, limited access storage area under the storage conditions defined by the sponsor. Where necessary, a temperature log must be maintained to make certain that the drug supplies are stored at the correct temperature.

The investigator / pharmacist/ investigational drug storage manager will receive the investigational drugs delivered by the sponsor when the following requirements are fulfilled:

- approval of the study protocol by the IRB / ethics committee,
- availability of a signed and dated clinical trial contract between the sponsor and the Head of Trial Centre,
- approval/notification of the regulatory authority, e.g. competent authority,
- availability of the curriculum vitae of the principal investigator,
- availability of a signed and dated clinical trial protocol or immediately imminent signing of the clinical trial protocol,
- if applicable, availability of the proof of a medical licence for the principal investigator,
- for the USA availability of the Form 1572.

The investigator / pharmacist / investigational drug storage manager must maintain records of the product's delivery to the trial site, the inventory at the site, the use by each patient and the return to the sponsor or alternative disposition of unused product(s).

These records will include dates, quantities, batch/serial numbers, expiry ('use by') dates and the unique code numbers assigned to the investigational product(s) and trial patients. The investigator / pharmacist / investigational drug storage manager will maintain records that document adequately that the patients were provided the doses specified by the CTP and reconcile all investigational product(s) received from the sponsor. At the time of return to the sponsor, the investigator / pharmacist / investigational drug storage manager must verify that all unused or partially used drug supplies have been returned by the clinical trial patient and that no remaining supplies are in the investigator's possession.

## 4.2 CONCOMITANT THERAPY, RESTRICTIONS, AND RESCUE TREATMENT

### 4.2.1 Rescue medication, emergency procedures, and additional treatment(s)

No rescue medication, emergency procedure or additional treatments are foreseen for this study.

### 4.2.2 Restrictions

#### 4.2.2.1 Restrictions regarding concomitant treatment

Intake of the following medications with the mentioned exceptions is prohibited during the entire duration of the trial including follow-up:

- a. Tricyclic antidepressants, other drugs which are active on the central nervous system (CNS) i.e. psychotropics (tricyclic antidepressants and monoamine oxidase inhibitors, mood stabilisers, neuroleptics, atypical antipsychotics, antiepileptics, benzodiazepines, other hypnotics or sedatives (including sedative antihistamines), muscle relaxants, or central analgesics, e.g., opioids.

**Note:** Zolpidem (10 mg/day), chloral hydrate (1 g/day), triazolam, quetiapine, temazepam and oxazepam if needed for sleep is allowed. If they are taken occasionally, then dosing on the night prior to cognitive testing is not allowed.

- b. Agents having central dopamine antagonist activity, i.e. reserpine, methyldopa, antiemetic's etc. However, the serotonin and combined serotonin/noradrenalin Re-Uptake Inhibitors (SSRIs/SNRIs) like fluoxetin, es-citalopram, citalopram, sertaline, venlafaxin, duloxetin are allowed, but paroxetine is excluded. Other antidepressant drugs without anticholinergic and without dopaminergic effects may be given as needed if the total daily dose was stable 8 weeks prior to randomization and is expected to be maintained for the duration of the trial.
- c. Intake of other phosphodiesterase inhibitors (for example theophyllin, roflumilast, sildenafil, tadalafil, vardenafil, avanafil).
- d. Intake of St. Johns wort, Carbamazepine, extracts from Gingko, artemisinin, enzalutamide, efavirenz, lopinavir, ritonavir, tipranavir, rifampicin as they are relevant CYP2C19 inducers
- e. Intake of prescribed drugs for treatment of AD including acetyl cholinesterase inhibitors (donepezil, galantamine, rivastigmine, tacrine, phenserine) and memantine)
- f. Use of medications that are known to be moderate or strong CYP1A2 inhibitors is not permitted. (For a list of moderate or strong CYP1A2 inhibitors, please consult the ISF Section 11 "Safety Information").

The drugs listed below may be used as needed:

Proprietary confidential information.

© 2017 Boehringer Ingelheim International GmbH or one or more of its affiliated companies. All rights reserved.

This document may not - in full or in part - be passed on, reproduced, published or otherwise used without prior written permission.

Non-prescription drugs or vitamins including medical nutrition formulations that have been initiated before visit 1 can be continued concomitantly during the study. However initiation of such medication after visit 1 is prohibited.

#### **4.2.2.2 Restrictions on diet and life style**

There are no other restrictions on diet, exercise, alcohol consume or smoking except that the patient's usual habits, including nicotine and caffeine intake, should be within acceptable daily amounts in discretion of the investigator and not be drastically changed throughout the study conduct.

Drastic weight-loss dieting during the study is not permitted.

### **4.3 TREATMENT COMPLIANCE**

Patients will be asked to bring all trial medication containers (with or without any remaining tablets) with them to each trial visit. The tablets will be counted and compliance will be calculated according to the formula:

$$\text{Compliance}(\%) = \frac{\text{Number of tablets actually taken since last tablet count}}{\text{Number of tablets which should have been taken in the same period}} \times 100\%$$

Compliance during the placebo run-in period should be between 75% and 120%.

Compliance during the randomized treatment period should be between 80 % and 120 %. Patients who are not compliant according to this definition should be carefully interviewed and re-informed about the purpose and the conduct of the trial.

## 5. VARIABLES AND THEIR ASSESSMENT

### 5.1 EFFICACY - CLINICAL PHARMACODYNAMICS

#### 5.1.1 Endpoint(s) of efficacy

The following efficacy measures are completed at the times shown in [section 6.2](#) and the [Flow Chart](#).

Primary endpoint:

- The primary endpoint is Neuropsychological Test Battery (NTB) response, defined as change from baseline in total z-score after 12-week treatment.

Secondary endpoints:

- Change from baseline in the ADCS-MCI-ADL (Alzheimer's Disease Cooperative Study/Activities of Daily Living for mild cognitive impairment) score after 12-week treatment.
- Change from baseline CDR-SB (Clinical Dementia Rating – Sum of Boxes) after 12-week treatment
- Change from baseline in ADAS-Cog11 (Alzheimer's Disease Assessment Scale-cognitive subscale) total score after 12-week treatment.

#### 5.1.2 Assessment of efficacy

Established neuropsychological assessments will be used to capture individual changes in memory, cognitive function and activities of daily living. Detailed instructions how to administer the assessments can be found in the respective user manuals which will be filed in the ISF.

The NTB consists of 9 validated components:

- Wechsler Memory Scale visual immediate (score range, 0-18)
- Wechsler Memory Scale verbal immediate (score range, 0-24)
- Rey Auditory Verbal Learning Test (RAVLT) immediate (score range, 0-105)
- Wechsler Memory Digit Span (score range, 0-24)
- Controlled Word Association Test (COWAT)

Proprietary confidential information.

© 2017 Boehringer Ingelheim International GmbH or one or more of its affiliated companies. All rights reserved.  
This document may not - in full or in part - be passed on, reproduced, published or otherwise used without prior written permission.

- Category Fluency Test (CFT)
- Wechsler Memory Scale visual delayed (score range, 0-6)
- Wechsler Memory Scale verbal delayed (score range, 0-8)
- RAVLT delayed (score range, 0-30). The RAVLT delayed measure is composed of delayed recall and recognition performance components that are summed to yield a score ranging from 0 to 30.

Raw scores on each of the 9 NTB tests will be converted to z-scores using the baseline means and standard deviations (SDs) for each test. The resultant z-scores will be averaged to obtain a total z-score, incorporating all 9 NTB tests [R13-2645].

ADCS-MCI-ADL

This is a functional scale based on the information provided by an informant/caregiver that describes the performance of patients in several activities of daily living for MCI patients. This is a 24 item scale with 6 items related to complex abilities. The sum score could range from 0 to 69. Higher scores indicate better function [R13-2647].

**CDR-SB** is obtained through semi structured interviews of patients and informants, and cognitive functioning is rated in 6 domains of functioning: memory, orientation, judgment and problem solving, community affairs, home and hobbies, and personal care. Each domain is rated on a 5-point scale of functioning as follows: 0, no impairment; 0.5, questionable impairment; 1, mild impairment; 2, moderate impairment; and 3, severe impairment (personal care is scored on a 4-point scale without a 0.5 rating available). The CDR-SB score is computed [R03-0748].

**ADAS-cog/11** is an 11-item cognitive subscale that objectively measures memory, language, orientation and praxis with a total score range of 0 to 70 [R96-2608].

[REDACTED] has been selected as service provider to support tasks related to the neuropsychological assessments.

The services of [REDACTED] include:

- Necessary Rater prequalification
- Central Rater training for neuropsychological assessments used as primary and secondary endpoints (online and at investigator meeting)
- Provision of Rater materials

Proprietary confidential information.

© 2017 Boehringer Ingelheim International GmbH or one or more of its affiliated companies. All rights reserved.

This document may not - in full or in part - be passed on, reproduced, published or otherwise used without prior written permission.

- Central Quality Review of Assessments

Details of rater prequalifications, Rater Training, Rater Materials (including Assessments) and of the Central review procedures will be available in a separate document filed in the ISF.

These members of the site staff conducting the neuropsychological assessments have to be adequately trained (either at the investigator training or individually) and training documentation has to be filed in the ISF. The training standards and standards for the conduct of the assessments will be defined for each assessment individually and can be found in the ISF. It is the responsibility of the Principal Investigator at the site to ensure proper training of all members of the site staff involved in the neuropsychological assessments.

## 5.2 SAFETY

### 5.2.1 Endpoint(s) of safety

No additional study specific important safety endpoints will be assessed in this study.

### 5.2.2 Assessment of adverse events

#### 5.2.2.1 Definitions of adverse events

##### Adverse event

An adverse event (AE) is defined as any untoward medical occurrence, including an exacerbation of a pre-existing condition, in a patient in a clinical investigation who received a pharmaceutical product. The event does not necessarily have to have a causal relationship with this treatment.

##### Serious adverse event

A serious adverse event (SAE) is defined as any AE which results in death, is immediately life-threatening, results in persistent or significant disability / incapacity, requires or prolongs patient hospitalisation, is a congenital anomaly / birth defect, or is to be deemed serious for any other reason if it is an important medical event when based upon appropriate medical judgement which may jeopardise the patient and may require medical or surgical intervention to prevent one of the other outcomes listed in the above definitions.

##### Intensity of adverse event

The intensity of the AE should be judged based on the following:

Mild: Awareness of sign(s) or symptom(s) which is/are easily tolerated

Moderate: Enough discomfort to cause interference with usual activity

Proprietary confidential information.

© 2017 Boehringer Ingelheim International GmbH or one or more of its affiliated companies. All rights reserved.

This document may not - in full or in part - be passed on, reproduced, published or otherwise used without prior written permission.

Severe: Incapacitating or causing inability to work or to perform usual activities

**Causal relationship of adverse event**

Medical judgment should be used to determine the relationship, considering all relevant factors, including pattern of reaction, temporal relationship, de-challenge or re-challenge, confounding factors such as concomitant medication, concomitant diseases and relevant history. Assessment of causal relationship should be recorded in the case report forms.

Yes: There is a reasonable causal relationship between the investigational product administered and the AE.

No: There is no reasonable causal relationship between the investigational product administered and the AE.

If a SAE is reported from a still blinded trial, the causal relationship must be provided by the investigator for all potential trial drugs, i.e. the BI trial drug and for all other trial drugs (i.e. any active comparator or placebo according to the trial design).

**Worsening of the underlying disease or other pre-existing conditions (except worsening of suicidal ideation and behavior)**

Worsening of the underlying disease or of other pre-existing conditions will be recorded as an (S)AE in the (e)CRF.

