### 3.3.4 Removal of patients from therapy or assessments

#### 3.3.4.1 Removal of individual patients

An individual patient is to be withdrawn from the trial if:

- The patient withdraws consent, without the need to justify the decision.
- The patient needs to take concomitant drugs that interfere with the investigational product or other study medications(s), refer to [section 4.2.2](#).
- The patient is no longer able to participate for other medical reasons (e.g. surgery, AEs, or other diseases).
- If a patient becomes pregnant during the trial, the investigational drug will be stopped, the patient will be discontinued from the trial and the patient will be followed up until birth or otherwise termination of the pregnancy.
- At visit 3, if the patient experiences sinus tachycardia (defined as resting pulse rate >100 BPM measured in supine position after a minimum of 5 minutes rest) at any time point up to 90±20 minutes post dose or if a pulse rate increase greater than 20 BPM over the pulse rate taken before the first dose administration (baseline) has persisted at 90±20 minutes post-dose. Pulse rate is generally to be measured in a supine position after 5 min rest. See also [section 5.2.5.2](#), and [section 6.2.2](#).
- The patient exhibits serious suicidality, in the clinical judgement of the investigator or according to criteria below:
  - Any suicidal behaviour (i.e. actual attempt, interrupted attempt, aborted attempt, or preparatory acts or behaviour)
  - Any suicidal ideation of type 4 or 5 in the C-SSRS (i.e. active suicidal thought with intent but without specific plan, or active suicidal thought with plan and intent)

A patient can be discontinued after discussion between sponsor and investigator if eligibility criteria have been violated, or if the patient fails to comply with the protocol (e.g. non-attendance at study assessments).

Patients who drop out during screening or during placebo run-in phase prior to randomization (Visit 3) will be considered as screening failure. For patients that screen fail, data will be collected for signed IC, demographics, AE, concomitant medications and randomization and recorded in the eCRFs. No further follow-up is required.

Patients who discontinue or withdraw from the study after randomization (Visit 3) will be considered as “early discontinuations” and the reason for premature discontinuation must be recorded in the eCRFs. The data will be included in the trial database and will be reported.

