### 5.2.2.2 Adverse event and serious adverse event reporting

All adverse events, serious and non-serious, occurring during the course of the clinical trial (i.e., from signing the informed consent onwards through the REP/follow-up period) will be collected, documented and reported to the sponsor by the investigator on the appropriate CRF(s) / eCRFs / SAE reporting forms. Reporting will be done according to the specific definitions and instructions detailed in the 'Adverse Event Reporting' section of the Investigator Site File.

For each adverse event, the investigator will provide the onset date, end date, intensity, treatment required, outcome, seriousness, and action taken with the investigational drug. The investigator will determine the relationship of the investigational drug to all AEs as defined in [section 5.2.2.1](#).

If a patient reports a change in visual perception or any vision-related AE, site staff must record the patient's verbatim description in the source documents to be reported in the eCRF. A local ophthalmology assessment will be required if any visual AE that is rated as moderate or severe by the subject or at the discretion of the PI. The ophthalmologist will act as a consultant to the Investigator and may offer advice on the proper management and treatment for the reaction.

The residual effect period (REP) for BI 409306 is 7 days and hence the time period for which adverse events will still be considered on-treatment, is  $\leq$  7 days following last intake of trial medication. All adverse events will be reported up until the last per protocol visit (follow-up visit) which is 28 days after the last dose of trial medication. The investigator does not need to actively monitor patients for adverse events once the clinical trial has ended. However, if the investigator becomes aware of an SAE(s) that occurred after the patient has completed the clinical trial (including any protocol required REP and / or follow-up), it should be reported by the investigator to the sponsor if considered relevant.

If not stipulated differently in the ISF, the investigator must report the following events 1) if using paper process SAE form via telephone/fax or 2) if available for the trial, using the electronic submission process (RDC) immediately (within 24 hours) to the sponsor: SAEs and non-serious AEs relevant to the SAE(s) and Adverse Events of Special Interest.

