Description of change	Reference to run-in was removed
Rationale for change	Clarification
Section to be changed	4.1.4
Description of change	“at approximately the same time every day” was added and “because they will receive new medication kits during the visits” was removed
Rationale for change	Clarification
Section to be changed	4.1.7
Description of change	Storage conditions were updated to better match the STORM document
Rationale for change	Clarification
Section to be changed	4.2.2.1
Description of change	“Agonist” Was changed to “Antagonist”
Rationale for change	A typographical error was corrected
Section to be changed	4.2.2.1
Description of change	St. Johns wort, Carbamazepine, extracts from Ginko, artemisinin, enzalutamide, efavirenz, lopinavir, ritonavir, tipranavir, rifampicin were added to the list of prohibited medications
Rationale for change	Relevant CYP2C19 inducers were excluded
Section to be changed	5.1.1 and 7.3.1
Description of change	NTB total score Was replaced by NTB total z-score
Rationale for change	Clarification
Section to be changed	5.1.1

Proprietary confidential information.

© 2017 Boehringer Ingelheim International GmbH or one or more of its affiliated companies. All rights reserved.

This document may not - in full or in part - be passed on, reproduced, published or otherwise used without prior written permission.

Number of global amendment	1
Description of change	Total CDR score was replaced by CDR-SB
Rationale for change	Clarification, a typo was corrected
Section to be changed	5.2.2.1
Description of change	The paragraph “Worsening of suicidal ideation and behaviour” was deleted
Rationale for change	Paragraph was included by error and contained misleading information
Section to be changed	5.2.2.2
Description of change	Wording on reporting of visual AEs moved from section 6.2.2 and changed to match project standards
Rationale for change	To be aligned with project standards
Section to be changed	5.2.5.2
Description of change	Section 10.1.1 was updated to project wording
Rationale for change	Clarification
Section to be changed	5.2.3
Description of change	Instructions for assessment of safety laboratory parameters were reworded to match project standards; Vitamin B12 and Folate were added to table 5.2.3: 1

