7.8.1.3 AE summaries

An overall summary of adverse events will be presented.

The frequency of patients with adverse events will be summarized by treatment, primary system organ class and preferred term (mention MedDRA levels to be displayed in the tables). Separate tables will be provided for patients with other significant adverse events according to ICH E3 ([4](#)), for patients with significant non-serious adverse events (only if these are defined for the project) and for patients with serious adverse events, for patients with AEs leading to discontinuation, and for patients with drug-related AEs.

The system organ classes will be sorted by default alphabetically, preferred terms will be sorted by frequency (within system organ class).

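### A heading in Protocol 5.2.2.1 excepts worsening suicidality from (S)AE recording, against the AE definition and its own text, and no specific recording rule replaces it

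*Protocol*

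**What the plan says.** **Recording rule.** Protocol 5.2.2.1 has a block headed "Worsening of the underlying disease or other pre-existing conditions (except worsening of suicidal ideation and behavior"). The sentence under it reads: "Worsening of the underlying disease or of other pre-existing conditions will be recorded as an (S)AE in the (e)CRF". The exception is in the heading only.

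**AE and SAE definitions.** The same section defines an AE as "any untoward medical occurrence, including an exacerbation of a pre-existing condition", with no carve-out for suicidality. The SAE definition covers death, life-threatening events, hospitalisation and important medical events, also without a carve-out.

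**Reporting.** Protocol 5.2.2.2 has all AEs collected from consent through follow-up. It sends to the sponsor within 24 hours "SAEs and non-serious AEs relevant to the SAE(s) and Adverse Events of Special Interest". Hepatic injury is the only AESI.

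**Withdrawal.** Protocol 3.3.4.1 lists as a reason for withdrawal: "The patient exhibits serious suicidality, in the clinical judgement of the investigator or according to criteria below". The criteria are any suicidal behaviour, or C-SSRS ideation of type 4 or 5. The reason for early discontinuation goes into the eCRF.

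**C-SSRS.** Protocol 5.2.5.3 responds to a positive finding on treatment with an interview, a decision on discontinuation and safety measures. It does not mention an (S)AE.

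**Analysis.** SAP 7.8.1.3 plans separate tables for serious AEs, drug-related AEs and "for patients with AEs leading to discontinuation". SAP 7.8.5.1 summarises the C-SSRS descriptively and separately.

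**The concern.** Suicidality is monitored prospectively in this trial (Protocol 2.3), and the C-SSRS is a named safety criterion in the synopsis. Yet worsening suicidality is the one kind of worsening that a heading in the AE section sets aside.

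A coordinator who takes the heading at face value would complete the C-SSRS, withdraw the patient if 3.3.4.1 applies, and open no AE page. Three things then follow:

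- The event gets no investigator causality rating, because that rating belongs to the AE record.
- It cannot become an SAE, because an SAE is by definition an AE that meets a seriousness criterion. It therefore does not enter the 24-hour route.
- It does not count in the SAP's AE tables or in the AE counts for disclosure.

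The patients concerned are those with earlier ideation or behaviour, in whom a causality judgement and a link to discontinuation would be most useful.

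**Working it through.** The plan gives no figure to reproduce. The check is a comparison of texts, with a short calculation of scale.

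**1. Do heading and rule agree?** No. The heading excepts worsening suicidality, and the operative sentence under it does not.

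**2. Does the exception fit the AE definition?** No. The definition includes exacerbation of a pre-existing condition without limit.

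**3. Does a specific rule take over what the heading sets aside?** No. The neighbouring sections show the gap:

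| Protocol section | Instruction to report clinically relevant post-baseline findings as (S)AEs |
|---|---|
| 5.2.5.1 Physical and neurological examination | Yes |
| 5.2.5.2 Vital signs | Yes |
| 5.2.5.3 C-SSRS | None |

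The 5.2.2.1 paragraph on changes in findings names vital signs, ECG, physical examination and laboratory results, but not the C-SSRS.

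**4. Where could the exception come from?** The Amendment 1 log in Protocol section 11 records that a 5.2.2.1 paragraph on this topic was removed, with the reason "Paragraph was included by error and contained misleading information". The heading appears to have kept a pointer to it. This explains the origin only; the inconsistency is in the current text.

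**5. Do general rules still reach these events?** Yes. The AE and SAE definitions and the collect-all rule in 5.2.2.2 apply, and an attempt that leads to hospitalisation meets the SAE definition directly. The sponsor's always-serious list is a weaker safeguard: it prompts a query on an AE already entered, so it cannot recover one never opened.

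**6. Who is affected?** Only patients whose suicidality pre-dates treatment. Exclusions 7 and 8 in 3.3.3 bar suicidal actions in the past 2 years and type 4 or 5 ideation in the past 3 months, which leaves room for older behaviour and for ideation of types 1 to 3. Protocol 5.2.5.3 also says that any suicidal behaviour or ideation excludes a patient, which would leave a smaller group. These two statements conflict.

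**7. Would another check catch a missed AE?** None is described. In SAP Table 6.2: 1, item E5 checks only that the C-SSRS was administered.

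**8. Scale.** One unrecorded event is 1/48 = 2.1% of an active arm, or 1/96 = 1.0% of placebo. The documents give neither the share of patients with earlier suicidality nor an event rate. As an illustration, assume a share of 5% to 10% and a worsening rate of 0.5% to 1% in that subgroup:

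- Patients: 288 × 0.05 ≈ 14; 288 × 0.10 ≈ 29.
- Expected events: 14 × 0.005 = 0.07; 29 × 0.01 = 0.29.
- Chance of at least one: 1 − 0.995^14 ≈ 7%; 1 − 0.99^29 ≈ 25%.

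A higher rate in this subgroup is plausible and would raise these figures. They also count events, not missed events: the text does not direct every site to leave the AE page blank.

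**The case against.** The strongest reply is that the exception is a parenthesis in a heading and that no sentence tells a site not to record such an event. The operative rule and the AE definition both point to recording. C-SSRS data are collected at every visit and summarised, and the reason for discontinuation is in the eCRF, so the event remains in the trial data. Protocol 5.2.2.2 also refers to reporting instructions in the Investigator Site File. Those instructions and the always-serious list are not available here, and they may close the gap.

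Much of this stands, and it rules out several stronger readings that a reader might infer:

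- *That nothing else in the protocol covers these events.* The general AE, SAE and collection rules do.
- *That suicidality leading to withdrawal is generally exempt.* The heading concerns pre-existing conditions. New-onset ideation or behaviour is outside it, and given the entry criteria many withdrawal events may be new onset.
- *That an assumed event rate can be applied to all 288 patients.* Only those with earlier suicidality fall under the exception.
- *That 3.3.4.1 contradicts the heading.* One governs withdrawal and the other recording; 3.3.4.1 is merely silent on AEs.
- *That the sponsor chose to leave suicidality out of AE data.* Nothing in the text shows such a decision.

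The reply does not remove the inconsistency. A written exception that contradicts the definition leaves each site to choose, and neither the C-SSRS summary nor the disposition reason carries a causality rating or feeds the AE tables.

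**Conclusion.** The point holds in limited form. The current text of 5.2.2.1 contradicts itself on whether worsening of pre-existing suicidality is recorded as an (S)AE, and no suicidality-specific rule resolves it. The general rules favour recording, so under-recording is possible but not directed. It depends on a site following the heading and on the Investigator Site File not correcting it, which cannot be checked.

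The number of affected events is probably small and cannot be derived from the documents; the 7% to 25% above rests wholly on assumed inputs. With 48 patients per active arm, however, one missing event could turn 2.1% into 0% in the table of AEs leading to discontinuation, and it could bypass the 24-hour route. The efficacy analyses do not depend on this. The change should be made, because it concerns a monitored safety outcome and costs little.

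**What to change.** 1. In Protocol 5.2.2.1, delete the parenthesis in the heading, so that the existing AE and SAE definitions apply to worsening suicidality as to any other worsening.
2. In 5.2.5.3, add the same line on reporting clinically relevant post-baseline findings as (S)AEs that 5.2.5.1 and 5.2.5.2 contain.
3. Reconcile the eligibility statements in 3.3.3 (exclusions 7 and 8) and 5.2.5.3. Which of them should stand is for the sponsor to decide.
4. Confirm that the AE reporting section of the Investigator Site File agrees, and tell sites of the correction.
5. Before database lock, list positive post-baseline C-SSRS responses and suicidality withdrawals against the AE records, and query any mismatch.

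Cost: a short text change, a site note, one listing, a few extra AE pages and possibly an additional expedited report. No treatment or withdrawal rule changes.
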